We are conducting a type 1 hybrid effectiveness-implementation study [6], whereby we concurrently compare two depression care management strategies, and systematically analyze barriers and facilitators to their adoption in the prenatal, pediatric primary care, and post-partum floor settings (Note: the secondary implementation analysis is the subject of another IRB application). Both intervention strategies (also referred to as comparators) are based on the construct of Screening, Brief Intervention, and Referral to Treatment (SBIRT) [7]. While both comparators share the same universal screening strategy, they differ in their brief intervention models, and in when mothers are referred to formal depression care. The first comparator is engagement-focused care management, in which the brief intervention is the Engagement Interview [8, 9]. In this model, bachelor-level care managers meet one to two times with mothers who screen positive for depression, and use techniques of shared decision making and motivation building to help mothers process the results of the screen; explore their related concerns; and connect with depression treatment services. The second comparator is Problem Solving Education (PSE), in which the brief intervention is a six-session cognitive-behavioral model, also delivered by bachelor-level providers [10, 11]. Whereas the Engagement Interview emphasizes referral to culturally relevant depression services, the PSE comparator offers immediate, low-level depression treatment onsite, and is followed by referral to further treatment if depressive symptoms persist. Over 12 months of follow-up, we will track patient-centered outcomes and engagement with care.

This study will be conducted in compliance with the protocol, applicable regulatory requirements, and BMC/BU Medical Campus Human Research Protection policies and procedures.

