3.2 Rationale and Purpose

Optimizing care coordination programs within the PCMH for populations with known health disparities is one of the IOM's top priorities for comparative effectiveness research [12]. Our trial is designed specifically to evaluate whether providing first-step depression treatment in the PCMH – delivered by peer providers – enhances uptake of services and improves outcomes among a screened population of pregnant and postpartum women; or whether it serves to delay more definitive care and symptom relief. Answering this question will allow a screened population of low-income and minority mothers to make informed decisions regarding how and where to receive depression care; and it will allow practice managers to make informed decisions regarding how to organize key components of the PCMH for both pregnant and postpartum women. Our ultimate goal is to reduce disparities in access to mental health care for low-income mothers; and to improve outcomes for them and their children. Our study also addresses a key evidence gap related to the USPSTF's latest recommendation on depression screening.

4 Objectives

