e. Child behaviors. Almost uniformly, our patient partners emphasize the impact of child behavior on their daily quality of life. For this, we will use the Child Behavior Checklist (CBCL-1.5/5) to assess a range of internalizing and externalizing child behaviors for children 1.5-5 years. We realize that not all participants will have children in this age range at all assessment time-points; thus, we have intentionally not powered the study with this measure.

An additional secondary outcome is engagement and retention with mental health services, as measured by NIMH's Collaborative Psychiatric Epidemiology Survey [18], which records all primary, specialty, and alternative sources of care. We categorize participants into those who engage with care; those retained in care; and those who receive evidence-based care. We use these definitions because of their association with a high likelihood of full symptom remission [5, 19, 20].

5 Study Design

We are conducting a randomized, parallel group comparative effectiveness trial of 230 pregnant and post-partum women with symptoms of depression. Women in one arm will receive Engagement-Focused Care Coordination, and women in the other will receive Problem Solving Education (PSE). Both intervention arms have been the subject of multiple BUMC IRB applications; all participant safety protocols have been tested over more than 10 years of related research.

In Engagement-Focused Care Coordination, the brief intervention is the Engagement Interview, which is designed to help engage participants in mental health care. The Engagement Interview is NOT a therapeutic or preventive intervention in and of itself. In delivering the Engagement Interview, Bachelor-level providers meet one to two times with women who screen positive for depression, and use techniques of shared decision-making to help mothers process the results of the screen; explore treatment options; and connect with formal mental health services. In PSE, problem solving sessions are one-on-one, workbook-based interactions that typically last 30 to 45 minutes. Sessions are delivered in the home, during lunch breaks from work, or in the clinic. A full course involves 6 sessions, delivered weekly or biweekly.

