12.3 Statistical Methods

Data Analysis Plan. We will report our results according to CONSORT guidelines. Because our aim is also for dissemination and implementation, we will analyze our data according to the RE-AIM (Reach, Effectiveness, Adoption, Implementation, Maintenance) framework, which addresses both internal and external validity.

- 1) **Reach.** We will record the number of mothers approached, screened, eligible, and refusing participation; compare demographics of those refusing to those participating; record subject attrition; and note all adverse events. We will compare baseline characteristics across comparators.
- 2) **Effectiveness.** We will conduct an intention-to-treat analysis to compare differences between comparators for all primary and secondary outcomes.

a) Main Effects. Our main effects analysis answers the question: **Which strategy is more effective at improving outcomes among a screened population of pregnant and postpartum women with depressive symptoms?**

- Patient Reported Outcomes: To assess depressive symptoms, we will employ Poisson or negative binomial regression techniques to compare incident rates of symptomatic episodes (QIDS ≥ 11) over 12 months of follow-up. We will use generalized estimating equations or mixed linear models to examine group-by-time effects on mean depressive symptom scores – as well as on mean scores of each of our other measures – as a function of intervention arm.

- Engagement and retention in care: Depending on the frequency of the observed outcomes, we will employ logistic or binomial regression techniques to compare the proportion of participants who meet the definition of engagement, retention, or receipt of evidence-based care. Among those engaging with care, we will employ Poisson or negative binomial regression techniques (depending on data dispersion) to compare number of mental health visits attended. We will compare treatment choices across groups. If data distribution assumptions are not met, we will consider nonparametric procedures or transformation of data. We will assess clustering by enrollment site and intervention practitioner, and if necessary use generalized mixed models to account for these effects. If randomization fails to produce balanced groups, we will add to our models potentially confounding variables, for which distributions are unequal across groups.

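### The number of mental health visits is compared only among women who engage with care, a group formed after randomization, and no visit comparison over all randomized women is planned

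*Combined protocol and SAP*

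**What the plan says.** The Effectiveness part of section 12.3 sets the general principle: "We will conduct an intention-to-treat analysis to compare differences between comparators for all primary and secondary outcomes". Its Main Effects question is "Which strategy is more effective at improving outcomes among a screened population of pregnant and postpartum women with depressive symptoms". Under engagement and retention in care, the first analysis covers everyone; it will "compare the proportion of participants who meet the definition of engagement, retention, or receipt of evidence-based care". The next sentence narrows the population: "Among those engaging with care, we will employ Poisson or negative binomial regression techniques (depending on data dispersion"), and the outcome there is the number of mental health visits attended.

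Section 4.2.2 makes engagement an outcome: "An additional secondary outcome is engagement and retention with mental health services". It defines three categories (engaged, retained, receiving evidence-based care) and does not name a visit count. The count appears only in section 12.3.

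Three statements show that engagement is expected to respond to the assigned arm:

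- Section 5 describes the Engagement Interview as an intervention "which is designed to help engage participants in mental health care".
- Section 3.1 says that PSE "is followed by referral to further treatment if depressive symptoms persist".
- Section 12.1 hypothesizes that PSE will spare some mothers, those with subsyndromal depression, a referral to formal care.

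No section gives a visit model that includes non-engagers, a combined two-part estimate, or a limit on how the engager-only contrast may be read.

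**The concern.** Randomization makes the two groups of mothers comparable at entry. It does not make those who later engage comparable. If PSE resolves milder cases without referral while the Engagement Interview steers women of all severities towards services, the engaged PSE women will on average be more symptomatic. They may then attend more visits because of who they are rather than because of what PSE did. The selection could also run the other way.

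Section 3.2 asks whether onsite first-step treatment "enhances uptake of services and improves outcomes among a screened population of pregnant and postpartum women". A count confined to engagers does not describe that population. A higher count among PSE engagers could also be taken as support for the section 12.1 hypothesis that PSE makes referrals more effective, when it reflects selection only.

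**Working it through.** **Is there a planned figure to reproduce?** No. The documents give no engagement rate, visit mean, power or sample size for this comparison. The reading of the text settles whether the gap exists. The calculations below only show its possible size, and every engagement and visit input in them is assumed. The 100 women per arm is the analyzable number in section 12.2. All ratios are PSE over Engagement Interview (EI).

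**Calculation 1: two types of women, by hand.** Let 40% of women engage under either arm, with a mean of 6 visits in both arms (no arm effect). A further 20% engage only under EI, with a lower mean m. Engagement is then 60% (EI) and 40% (PSE).

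- Mean among EI engagers = (0.40 × 6 + 0.20 × m) / 0.60. Mean among PSE engagers = 6.
- m = 6: EI mean 6.00; engager-only ratio 1.00; all-women ratio 2.40/3.60 = 0.67.
- m = 3: EI mean 3.00/0.60 = 5.00; engager-only ratio 6/5.00 = 1.20; all-women ratio 2.40/3.00 = 0.80.
- m = 2: EI mean 2.80/0.60 = 4.67; engager-only ratio 6/4.67 = 1.29; all-women ratio 2.40/2.80 = 0.86.

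In 4,000 simulated trials with overdispersed counts, the engager-only test at nominal 5% rejected in 6.3%, 21.3% and 30.9% of trials for m = 6, 3 and 2. With 50% engagement in both arms it rejected in 5.7%.

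**Calculation 2: a continuous severity gradient.** Let severity s be standard normal in both arms. The probability of engaging is logistic in s with slope b, and the intercept is set to give the stated rate. Mean visits if engaged are exp(1.2 + g·s) in both arms, so there is no arm effect at equal severity. The engager-only ratio is the ratio of E[P(engage | s) · exp(1.2 + g·s)] / P(engage) between arms, by numerical integration.

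| Engagement EI vs PSE | Ratio, b = 1, g = 0.5 | Ratio, b = 0.5, g = 0.25 |
|---|---|---|
| 50% vs 40% | 1.043 | 1.012 |
| 60% vs 40% | 1.084 | 1.024 |
| 70% vs 40% | 1.125 | 1.036 |

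- At 60% vs 40% with the steeper slopes, engagers average 4.36 (EI) and 4.72 (PSE) visits, and 4.72/4.36 = 1.08. Engaged PSE women are 0.17 SD more severe.
- With the rates reversed between arms, the steeper-slope ratios become 0.959, 0.923 and 0.889.
- Equal engagement rates do not by themselves remove the bias. At 50% in both arms, engagement slopes of 1.5 (PSE) vs 0.5 (EI) give 1.127 (1.069 with g halved), 1.25 vs 0.75 give 1.060 (1.033), and 0.5 vs 1.5 give 0.887.
- All-women ratio at 60% vs 40%: (0.40/0.60) × 1.084 = 0.72; with halved slopes, (0.40/0.60) × 1.024 = 0.68.

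**False rejection.** These figures come from 20,000 simulated trials per scenario, 100 women per arm, with a robust SE and a nominal 5% test. Overdispersed means added gamma heterogeneity of variance 1.

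| Scenario | Poisson given s | Overdispersed |
|---|---|---|
| Same rate and gradient in both arms | 5.4–5.8% | 5.6–6.7% |
| 50% vs 40%, steeper slopes | 6.4–6.8% | 6.4–6.7% |
| 60% vs 40%, steeper slopes | 9.3–9.6% | 7.4–7.7% |
| 70% vs 40%, steeper slopes | 14.5–14.9% | 8.4–8.7% |
| Halved slopes, the three rate pairs | 5.5–6.7% | 6.0–6.6% |
| 50% in both, slopes 1.5 vs 0.5 | 15.0–15.4% | 9.4–9.8% |
| 50% in both, slopes 1.25 vs 0.75 | 7.7–7.9% | 6.7–7.0% |

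The first row is the benchmark, because the test itself is slightly liberal at this sample size.

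**When the bias is zero.** In this model it vanishes if severity does not affect visits, if severity does not affect engagement in either arm, or if both the engagement rate and its severity gradient are the same in the two arms.

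**The case against.** The visit count is a follow-on analysis. Section 4.2.2 does not list it, so the intention-to-treat sentence may not reach it, and a flat contradiction within section 12.3 is not established. That stands. It lowers the priority, but the plan still sets out a between-arm regression under Main Effects.

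Uptake in the screened population is already answered by the proportions engaged, retained and receiving evidence-based care, which are compared over participants. That also stands.

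The proportion engaged and the count among engagers are the two halves of a two-part analysis, and a reader can multiply them, as was done above to get 0.72. This recovers the point estimate. It does not give an interval or a test, and the plan does not warn that the second half alone is not a treatment effect.

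The section 12.1 hypothesis about more effective referrals concerns women who need care, and a count over all women does not test it. This is correct. The engager-only contrast does not test it cleanly either, because engaging is not the same as needing care and depends on the arm.

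Section 12.3 would add covariates if groups are unbalanced. That clause is triggered by a failure of randomization. It does not address selection after a successful one, and symptoms arising after baseline can also drive engagement.

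Finally, the inputs are assumed and most of the resulting biases are small. That is fair, and the verdict says so.

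**Conclusion.** The concern holds. The plan tests visit counts in a subgroup defined by an outcome that the arms are expected to change, and it offers no comparison over all randomized women. Confidence in this reading is high.

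The size and direction of the bias cannot be known from the documents. Under the severity-gradient assumptions it is negligible to modest: about 1–4% with weak gradients and 4–13% with steeper ones. Under the two-type assumption it can be larger, with a ratio of 1.20 to 1.29 at 60% vs 40% when the extra engagers average 3 or 2 visits. The more practical risk is that the engager-only and all-women counts point in opposite directions.

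This is a change that should be made because it is cheap. It does not threaten the primary QIDS analyses, the sample size or the engagement proportions.

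**What to change.** In section 12.3, make the between-arm comparison of visits over 12 months in all randomized women, with non-engagers counted as zero. Use either a negative binomial model with robust SE or a two-part model combined into one marginal mean ratio with its confidence interval. Treat women whose visit data are missing as missing, not as zero; section 12.2 expects 15% attrition. Report the result beside the proportion engaged. Keep the engager-only count as a descriptive summary with no causal between-arm test.

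The cost is SAP wording. Section 9 already schedules assessment of service use for every participant at each two-monthly follow-up.

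There are two downsides. First, the all-women count mixes whether women engage with how much care they use, and fewer visits may mean averted need, so it must be read with the proportion engaged and the QIDS results. Second, it is less precise: at 60% vs 40% the SE of the log ratio is about 0.20 against 0.14 among engagers, or 0.31 against 0.27 with overdispersion.

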Those opting to participate in the trial will meet with a study team member for written informed consent and for determination of final eligibility. Study participants must have no current source of mental health care and speak English or Spanish. Following confirmation of eligibility, the study staff member will administer a baseline survey that includes valid and reliable scales for depression and anxiety symptoms, trauma history and post-traumatic stress symptoms, history of receipt of mental health care, co-morbid substance use, and participant demographics. Mothers will then be randomized 1:1 to the two comparators, and followed for 12 calendar months.

Total Study Duration:	Three years
Subject Participation Duration:	One year

3 Background/Rationale & Purpose

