4.2 Study Outcome Measures

4.2.1 Primary Outcome Measures

Each subject will have 12-months of follow-up. All outcomes will be assessed at 2-month intervals.

Our primary outcome measure is depressive symptomatology, as measured by the QIDS – and operationalized as an incident rate of moderate to severe episodes over time and as symptom trajectories.

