We will employ stratified, blocked 1:1 randomization, the unit of which will be the mother. All investigators and data collectors will be blinded to study allocation. Randomization will occur independently at each clinic site (Prenatal Clinic, Pediatric Primary Care, Postpartum Unit). We will further stratify randomization by whether or not participants have previously received medication or therapy for depression, as this will likely impact treatment choices. Randomizing in blocks of randomly varying sizes of 2 and 4 within stratum will ensure balance between study arms.

Follow-up data collection will occur over the course of 12 month, with repeated collection of patient-centered outcomes by self-reported to research team members masked to intervention arm.

6 Potential Risks and Benefits

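### The episode-rate analysis of the primary outcome commits no baseline covariate, not even the randomisation strata, and so gives up some precision that costs almost nothing to keep

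*Combined protocol and SAP*

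**What the plan says.** Section 4.2.1 gives the primary outcome two forms; depressive symptoms on the QIDS are "operationalized as an incident rate of moderate to severe episodes over time and as symptom trajectories". For the first form, Section 12.3 (Main Effects) says "we will employ Poisson or negative binomial regression techniques to compare incident rates of symptomatic episodes". For the second it says "We will use generalized estimating equations or mixed linear models to examine group-by-time effects on mean depressive symptom scores". Neither sentence names a baseline covariate.

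The one rule for adding baseline variables reads: "If randomization fails to produce balanced groups, we will add to our models potentially confounding variables, for which distributions are unequal across groups". It has no list of candidate variables and no threshold for calling distributions unequal. It stands in the bullet on engagement and retention, although its reference to the models in general suggests a wider reach. The same bullet treats site conditionally: "We will assess clustering by enrollment site and intervention practitioner, and if necessary use generalized mixed models to account for these effects". The other mention of covariates in Section 12.3, under heterogeneity of treatment effect, concerns repeated symptom measures during follow-up and is not a baseline adjustment.

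Section 5 makes both site and prior treatment randomisation strata: "Randomization will occur independently at each clinic site (Prenatal Clinic, Pediatric Primary Care, Postpartum Unit"), and "We will further stratify randomization by whether or not participants have previously received medication or therapy for depression, as this will likely impact treatment choices". On other baseline information, the synopsis says that study staff "will administer a baseline survey that includes valid and reliable scales for depression and anxiety symptoms" before randomisation, without naming the scale there. Section 7.1 requires an EPDS score of at least 10, so every randomised woman has one.

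**The concern.** A baseline variable that predicts the outcome reduces the variance of the treatment comparison whether or not the arms happen to differ on it. Making adjustment wait for a visible imbalance therefore ties it to the wrong condition. In most trials the trigger will not fire and the reported standard error stays as large as without the covariate. The rule is also unlikely ever to bring in the two strata, because blocked randomisation within strata is there to balance them. The plan itself expects prior treatment to influence treatment choices, yet that factor does not appear in the analysis.

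If the rule does not reach the depression models, those models have no covariate rule at all. On either reading, nothing is committed for the episode rate. What is at stake is precision in a comparison whose sample size leaves little to spare on the plan's own calculation.

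**Working it through.** **1. The plan's own figure.** Inputs from Section 12.2: 100 analysable women per arm, 1.2 against 0.8 episodes per six assessments, two-sided alpha 0.05. The standard error of the log rate ratio is √(1/(100×1.2) + 1/(100×0.8)) = √0.02083 = 0.144. Power is Φ(ln 1.5/0.144 − 1.96) = Φ(2.81 − 1.96) = 80.2%, and the required size is 99.5 per arm. The stated 80% reproduces, for a two-group comparison without covariates.

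**2. Why a covariate can help.** If all women in an arm shared one Poisson rate, adjustment would gain nothing. Section 12.2 gives a within-woman QIDS correlation of 0.6 at two months or more, which implies that women differ strongly.

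**3. What correlation the EPDS might have.** The documents give none, so two inputs are assumed: 10 to 30% of women screen positive, and the correlation between EPDS and follow-up score is r = 0.4 to 0.6 before selection. Restriction to EPDS ≥ 10 shrinks it to r′ = r·u/√(1 − r² + r²u²), where u² is the variance of a standard normal truncated to the positive screens: 0.169, 0.219 and 0.265 at 10, 20 and 30% positive.
- r = 0.4: r′ = 0.18, 0.20, 0.22
- r = 0.6: r′ = 0.30, 0.33, 0.36

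**4. Effect on the episode-rate analysis.** Simulation: a latent normal score at six visits with correlation 0.6, thresholds set to give mean counts of 1.2 and 0.8, 100 women per arm, Poisson regression with robust variance, 40,000 trials per setting. The variance/mean ratio of the counts is 2.28. Equivalent size = 100/(1 − variance cut).

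| Assumed within-sample correlation | Cut in variance of log rate ratio | Equivalent women per arm |
|---|---|---|
| 0.20 | 3.5% | 104 |
| 0.30 | 7.6% | 108 |
| 0.36 | 11.3% | 113 |
| 0.45 | 18.4% | 123 |

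Repeat simulations of 4,000 to 5,000 trials gave 2 to 4% at 0.2, 9 to 12% at 0.36 and 18 to 19% at 0.45. The median log rate ratio was −0.405 unadjusted and −0.406 to −0.412 adjusted, so the gain is essentially precision and not a shift in what is estimated.

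**5. How much an imbalance trigger recovers.** At correlation 0.36, adjusting always adds 4.7 percentage points of power (44.9% to 49.6%). Adjusting only when the baseline difference has p < 0.05 adds 0.1 point, and p < 0.20 adds 0.6. At 0.45 the three figures are 8.4, 0.3 and 1.3 points. Only the differences matter here; the low absolute level comes from the simulated overdispersion.

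**6. Type I error** (20,000 null trials per setting): 4.7 to 4.9% unadjusted and 4.7 to 5.1% with pre-specified adjustment. If an analyst takes the better of the two results, but only when baseline looks unequal (p < 0.05 to p < 0.30), it is 4.8 to 5.7%.

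**The case against.** The strongest reply is that this is a preference about efficiency and not an error. The unadjusted analysis is valid, the plan's power figures reproduce, and the gain that needs no unconfirmed data is small: 4 to 13 women's worth per arm, on two assumed inputs. Site is not ignored either. Clustering by site is to be assessed, and the analysis by pregnancy or postpartum status overlaps with it. All of this stands and limits the weight of the point. It does not supply a committed covariate for the episode-rate model.

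Four stronger readings are tempting, and the documents do not support them.

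- *The missing covariates leave the trial badly underpowered.* The power of about 45% in the simulation comes from overdispersion, a separate matter. Only the variance cut belongs to this point.
- *The vague rule inflates type I error.* Used as written, it adds at most 0.9 percentage points.
- *A baseline QIDS would cut the variance by a third.* That figure (32.5%, or 148 per arm) needs a correlation of 0.6 within this EPDS-selected sample. The documents' 0.6 is between QIDS scores in earlier longitudinal data, and the readable text does not confirm a baseline QIDS. Suppose 0.6 holds before selection, with EPDS–QIDS correlations of 0.6 to 0.8 and EPDS–outcome correlations of 0.4 to 0.5 (all assumed). Selection then lowers it to about 0.44 to 0.53.
- *The QIDS trajectory test loses power too.* With complete follow-up data, a time-constant baseline covariate leaves the group-by-time test unchanged: 78% and 90% power at correlations 0.6 and 0.7, against the plan's 77% and 89%. The plan does not say how a baseline QIDS would enter that model, so no loss there can be attributed to it.

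**Conclusion.** The point holds for the episode-rate form of the primary outcome. Section 12.3 commits no baseline covariate, relies on an undefined imbalance rule, and does not carry both randomisation strata into the model. The consequence is forgone precision, not bias. With the screening EPDS it is about 4 to 12% of the variance of the log rate ratio, assuming a within-sample correlation of about 0.2 to 0.36. With a baseline QIDS, if one is taken, it is about 8 to 18% at assumed correlations of 0.3 to 0.45, and more only if the correlation among these selected women is higher. All these figures assume the between-woman heterogeneity that the plan's correlation of 0.6 implies. Negative binomial models were not simulated. The effect of leaving out the strata cannot be quantified from the documents. This is an improvement worth making because it is nearly free; the planned analysis remains interpretable without it.

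**What to change.** In Section 12.3, replace the imbalance sentence, as far as it concerns the depression analyses, with a fixed specification.

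- **Episode-rate model:** arm, site (three levels), prior depression medication or therapy (yes/no), and one baseline depression score (baseline QIDS if taken, otherwise the screening EPDS). Use these whatever the observed balance, with a robust variance.
- **QIDS mean-score model:** include the two strata as well.
- **Sensitivity analyses only:** the unadjusted result, and any adjustment prompted by observed imbalance.

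The Schedule of Events, which is not readable in this text, should be checked for a baseline QIDS, and the choice of score fixed before unblinding. The cost is wording and a few extra model parameters; the strata and the EPDS exist for every randomised woman. One limitation remains: in the outpatient setting the EPDS is taken before the baseline meeting (Section 9), so it may predict less well than a same-day score.
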